The study will be conducted in the Republic of Sudan, which is located in northeastern Africa. It is bordered by North is Bordered by Egypt, Northeast Has a coastline along the Red Sea, East Shares borders with Eritrea and Ethiopia, South Bordered by South Sudan, Southwest Borders the Central African Republic, West Shares a border with Chad, Northwest Bordered by Libya. It has 18 states: Blue Nile, Central Darfur, East Darfur, Gedaref, Gezira, Kassala, Khartoum (the capital), North Darfur, North Kordofan, Northern, Red Sea, River Nile, Sinnar, South Darfur, South Kordofan, West Darfur, West Kordofan, White Nile. This number is after the secession of South Sudan, which occurred on July 9, 2011.

Sudan is the third largest country in Africa, covering an area of approximately 1,886,068 square kilometers (728,215 square miles). The population in July 2015 was an estimated 36.1 million people, according to recent estimates, the population of Sudan will reach approximately 49 million people in 2024. Sudan is considered the 31st most populous country in the world. (1)

Study Population:

The study population consists of Sudanese general practitioners (GPs) working in primary health care centers across different states in Sudan.

Inclusion Criteria:

Participants must meet the following criteria:

1. Sudanese nationality
2. Age above 23 years
3. General practitioner
4. Currently working in primary care centers
5. Residing in Sudan during the study period

Exclusion Criteria:

Individuals who do not meet the following criteria will be excluded:

1. Non-Sudanese

2. Age below 23 years
3. Non-general practitioners
4. Not working in primary care centers
5. Not residing in Sudan during the study period

Sample Size Calculation:

The sample size will be calculated using the following formula

$$\text{Sample Size} = [z^2 * p(1-p)] / e^2$$

z = z-score corresponding to the desired confidence interval, at 95% Confidence Level
Z = 1.96.

e = desired margin of error, which is a 5% confidence limit.

p = estimated proportion of population with the characteristic of interest **p** = 0.5 is used for maximum variability

the sample size was calculated as 211

Data collection:

Sampling: The study will utilize multistage sampling technique to select the participants. whereby, In the first stage, the 18 states will be clustered into 5 main areas. Then, the participants will be sampled conveniently from within these areas due to accessibility challenges.

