Ethical consideration: consent will be obtained from each participant, and personal identifying data are excluded from the questionnaire to ensure privacy.

Data collection tool: self-administered questionnaire designed through Google Forms to collect facts from the selected participants. The questionnaire captured applicable factors related to dermatology, knowledge, attitudes, and practices.

Several 211 questionnaires were collected, divided equally into five regions in Sudan: East, North, South, West, and Central

Data Analysis:

- **Data Description:**

Mean, median, frequency, and standard deviation will be used to express for the descriptive analysis to display the knowledge and attitude scores.

- **Software:**

Retrieved data will be analyzed using the statistical software package SPSS version 21

- **Statistical tests:**

[figure not shown]
We will use Chi-square test and Spearman correlation tests to examine for the association and correlation, and T- test, Kruskal-Wallis and Mann-Whitney U tests to explore the differences between variables depending on the normality of data. 0.05 is chosen as the cut-off point of significance for the p-value.

- **Handling Missing Data:**

Missing data will be handled using available case analysis (pairwise deletion).

- **Presentation of Results**

The data will be presented using graphs and tables to present the key findings.

Time frame:

References:

3. Kibar Öztürk M. Skin diseases in rural Nyala, Sudan (in a rural hospital, in 12 orphanages, and in two refugee camps). *Int J Dermatol.* 2019 Nov;58(11):1341-1349. doi: 10.1111/ijd.14619. Epub 2019 Sep 9. PMID: 31498882.

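### The sample-size formula and all listed tests assume independent respondents, although convenience recruitment may bring in several GPs per centre; if it does, the 5-point margin fails and between-centre or between-region tests reject too often.

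*Combined protocol and SAP*

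**What the plan says.** The Sample Size Calculation section of the combined protocol and SAP uses z²p(1−p)/e², with "z = z-score corresponding to the desired confidence interval, at 95% Confidence Level", z = 1.96, "e = desired margin of error, which is a 5% confidence limit", and a p for which "0.5 is used for maximum variability". It then reports that "the sample size was calculated as 211".

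The sampling paragraph under Data collection labels the design multistage. It says "In the first stage, the 18 states will be clustered into 5 main areas", and that within them "the participants will be sampled conveniently from within these areas due to accessibility challenges". The same section says the questionnaires are spread equally over five regions. The Inclusion Criteria require that each GP be "Currently working in primary care centers". No limit is set on respondents per centre, and the plan does not say that the form records the centre.

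Under Data Analysis the plan says "We will use Chi-square test and Spearman correlation tests to examine for the association and correlation", adds t, Kruskal-Wallis and Mann-Whitney tests for differences, and sets the significance level at 0.05. It mentions no design effect, ICC, cluster-robust method, mixed model or survey analysis.

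**The concern.** The formula gives the precision of a proportion under simple random sampling, and all five tests in their usual form take the answers as independent. All five areas contribute respondents, so the areas act as strata rather than sampled clusters. The clustering that matters would arise below that level. When recruitment follows accessibility, one reachable centre can easily supply several GPs. Colleagues there share case mix, local training and working conditions, and their scores may resemble each other.

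Two things are then at stake. The stated margin of error would understate the uncertainty. Comparisons of groups made up of whole centres or whole regions would produce false positives more often than the nominal 5%.

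**Working it through.** **Plan's own figure.** n = 1.96² × 0.5 × 0.5 / 0.05² = 384.16, so 385. The stated 211 does not follow from these inputs. At 211, with full independence, the margin is 1.96 × √(0.25/211) = 0.0675, or 6.7 points. That shortfall is a separate problem. Both sizes are carried below to show what clustering adds.

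**Inputs not in the documents (assumed).** m is the number of responding GPs per centre and ICC is the correlation between colleagues. The main range is m = 5 to 10 with ICC 0.05 to 0.10; m = 1 to 3 is shown because the documents allow it equally.

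**Formulas.** Design effect DE = 1 + (m − 1) × ICC. Effective n = 211/DE. Margin = 1.96 × √(0.25 × DE/n).

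| m | ICC | DE | Effective n of 211 | Margin at 211 (points) | Margin at 385 (points) |
|---|---|---|---|---|---|
| 1 | any | 1.00 | 211 | 6.7 | 5.0 |
| 2 | 0.05 | 1.05 | 201 | 6.9 | 5.1 |
| 3 | 0.05 | 1.10 | 192 | 7.1 | 5.2 |
| 5 | 0.05 | 1.20 | 176 | 7.4 | 5.5 |
| 5 | 0.10 | 1.40 | 151 | 8.0 | 5.9 |
| 10 | 0.05 | 1.45 | 146 | 8.1 | 6.0 |
| 10 | 0.10 | 1.90 | 111 | 9.3 | 6.9 |

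Holding a 5-point margin would need 384.16 × DE respondents: 461 at DE 1.2 and 730 at DE 1.9.

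**Effect on the tests.** For a two-group factor fixed by centre, the true level of a nominal 5% test is roughly 2 × [1 − Φ(1.96/√DE)]. This was checked by simulating scores with no true difference: about 210 respondents, normal scores with a centre effect, 4,000 runs per row.

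| m | ICC | Approximation, centre-level factor | Mann-Whitney, centre-level factor | Kruskal-Wallis, five regions | Mann-Whitney, factor random between individuals | Mann-Whitney, factor balanced within centres |
|---|---|---|---|---|---|---|
| 2 | 0.05 | 5.6% | 5.8% | 6.1% | 5.2% | 4.0% |
| 3 | 0.05 | 6.2% | 6.1% | 7.4% | 4.7% | 4.6% |
| 5 | 0.05 | 7.4% | 6.9% | 8.9% | 5.2% | 4.9% |
| 5 | 0.10 | 9.8% | 9.2% | 14.0% | 4.9% | 4.2% |
| 10 | 0.10 | 15.5% | 16.0% | 28.5% | 5.3% | 3.4% |

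A separate simulation of the centre-level Mann-Whitney test (n = 210, 8,000 runs) gave 7.2% for m = 5 with ICC 0.05, about 10% for both m = 5 with ICC 0.10 and m = 10 with ICC 0.05, and 15.2% for m = 10 with ICC 0.10. The inflation depends on where the factor varies: it appears for centre-level and region-level groupings and not for individual-level ones.

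**The case against.** A reader might infer that GPs will certainly arrive in groups from the same centres. The documents do not say so. The centre is an eligibility condition, not a sampling unit, and each GP completes an individual online form. With one GP per centre nothing changes, and with two or three at ICC 0.05 the margin at 211 rises only to 6.9 to 7.1 points. This objection stands: grouping is likely, not established, and its size cannot be fixed from the documents.

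A reader might also infer that every p-value is too small. The simulations contradict that. Factors that vary between individuals, such as years of experience, keep a rate near or below 5%. The plan does not list its explanatory variables, so how many tests are exposed is unknown. Region is the one grouping it names, and centres nest wholly within it.

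Nor do the documents support saying that the reported intervals will be too narrow, because none are planned. The descriptive output is means, medians, frequencies and standard deviations. The affected quantity is the 5-point margin.

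Finally, that margin already fails at 211 on arithmetic alone, and convenience sampling carries selection bias that no design effect captures. Both are true. But moving to 385 would not by itself secure 5 points if answers are clustered, and the plan neither justifies independence nor allows for its failure.

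**Conclusion.** The point holds conditionally. A design described as multistage, with convenience recruitment, is sized and tested as if respondents were a simple random sample. If GPs share centres and their answers correlate positively, clustering adds up to 1.9 points to the margin at n = 385 (5.0 to 6.9) and up to 2.6 points at n = 211 (6.7 to 9.3), for design effects of 1.0 to 1.9. A centre-level Mann-Whitney test would reject in about 7% to 15% of null cases with 5 to 10 GPs per centre and ICC 0.05 to 0.10. A five-region Kruskal-Wallis test would be worse, at 8.9% to 28.5% across the three simulated scenarios with 5 to 10 GPs per centre. Tests of individual-level factors need no material correction.

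All of these sizes rest on assumed values of m and ICC, so they are illustrations and not estimates. The gap should be closed, but it does not invalidate the survey.

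**What to change.** First correct the base calculation and state how GPs are reached.

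**If the form is still open:** add a non-identifying centre code and the state. Report respondents per centre and the ICC for each score. Analyse centre-level and region-level factors with cluster-robust or mixed models. Specify a small-number-of-clusters correction, since at 10 GPs per centre there would be only about 211/10 ≈ 21 centres, and uncorrected robust standard errors tend to be too small. Restate the margin multiplied by √DE.

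**If centre was not recorded:** the plan describes the questionnaires in the past tense, so collection may be over. In that case drop the 5% claim, report the margin over a stated range of design effects starting at 1.0 (for example 1.0 to 1.9), and label between-region and centre-level p-values as possibly too small.

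**In either case:** say that no design effect corrects the selection bias of convenience sampling.

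**Cost:** up to two items on the form (centre code and state) and a model in place of the simple tests for the affected factors. The results will have wider intervals and a less favourable stated margin. A centre code combined with state could identify GPs in small centres, which would conflict with the plan's privacy statement, so codes should be arbitrary and small centres should not be reported individually.
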